**Table 4 Lenalidomide Dose Reduction**

Dose Level	Lenalidomide Dose
Starting Dose Level	25 mg
First Dose Reduction	20 mg
Second Dose Reduction	15 mg
Third Dose Reduction	10 mg
Fourth Dose Reduction	5 mg

### 6.3 Dexamethasone

#### Dexamethasone Dose Modifications

CONFIDENTIAL

This document is confidential. Do not disclose or use except as authorized.

Premedication with dexamethasone is required prior to all elotuzumab infusions. If there are clinically significant, intolerable  $\geq$ Grade 3 adverse events attributed to dexamethasone (given as a premedication) treatment may be delayed until recovery to  $\leq$  Grade 2 at the discretion of treating investigator. For adverse events that are considered to be possibly, probably or definitely related to dexamethasone, the following criteria for retreatment and dose modification should be followed. The treating investigator should determine the clinical significance and attribution of the toxicity to dexamethasone. If toxicity is unlikely or not related to dexamethasone, do not omit or reduce therapy. Patients may continue on study if oral dexamethasone has been permanently discontinued

Patients who have not experienced an infusion reaction related to elotuzmab and have experienced an adverse event attributable to dexamethasone may have their premedication of dexamethasone decreased after completion of cycle 1 at the discretion of the treating investigator and after discussion with the overall PI.

CTCAE 4.0 Category	CTCAE Grade	Dexamethasone Dose Modification
Hyperglycemia  Treat with oral medication or insulin at discretion of treating investigator	Grade 1	Continue to treat- Do NOT OMIT and DO NOT REDUCE therapy
	Grade 2	Hold dexamethasone until $<$ Grade 2 and resume at same dose level at the discretion of the treating investigator
	Grade 3	Hold dexamethasone until $<$ Grade 2  Resume therapy with one dose level reduction at the discretion of the treating investigator
	Grade 4	Hold dexamethasone until $<$ Grade 2  Resume therapy with one dose level reduction
Symptomatic pancreatitis	Any Grade	Discontinue dexamethasone permanently
OTHER	Grade 1 or 2	Continue to treat- Do NOT OMIT and DO NOT REDUCE therapy
	Grade 3	Hold dexamethasone until $\leq$ Grade 2  Resume therapy with one dose level reduction
	Grade 4	Hold dexamethasone $\leq$ Grade 2  Resume therapy with one dose level reduction

CONFIDENTIAL

This document is confidential. Do not disclose or use except as authorized.

**Table 5 Dexamethasone dose reduction**

**Total Dexamethasone Dose Administration for Patients with none or Prior Grade 1 Infusion Reaction**

Dose Levels	Week with Elotuzumab		Week Without Elotuzumab*	
	PO	IV	PO	IV
Starting Dose Level	32	8	40	0
First Dose Reduction	28	8	20	0
Second Dose Reduction	28	8	10	0

\* During Maintenance, patients only receive dexamethasone on Day 1

**Total Dexamethasone Dose Administration for Patients with Prior Grade 2 Infusion Reaction**

Dose Levels	Week with Elotuzumab		Week Without Elotuzumab*	
	PO	IV	PO	IV
Starting Dose Level	30	10	40	0
First Dose Reduction	28	10	20	0
Second Dose Reduction	28	10	10	0

\* During Maintenance, patients only receive dexamethasone on Day 1

**Total Dexamethasone Dose Administration for Patients Prior Grade 3 or recurrent Grade 2 Infusion Reaction**

Dose Levels	Week with Elotuzumab		Week Without Elotuzumab*	
	PO	IV	PO	IV
Starting Dose Level	22	18	40	0
First Dose Reduction	16	18	20	0
Second Dose Reduction	16	18	10	0

\* During Maintenance, patients only receive dexamethasone on Day 1

\*\* If patient is intolerant of dexamethasone, after discussion with overall PI, oral dexamethasone may be omitted at any dose level.

#### **6.4 Guidelines for Elotuzumab Infusion in Subjects with Infusion Reactions**

##### **6.4.1 Grade 1 Infusion Reaction**

Grade 1 elotuzumab infusion-related reactions by definition do not require intervention; however, increased monitoring is recommended.

CONFIDENTIAL

This document is confidential. Do not disclose or use except as authorized.

#### 6.4.2 Grade $\geq$ 2 Infusion Reaction

Infusion reactions during the elotuzumab infusion: For a Grade  $\geq$  2 elotuzumab infusion- related reaction, the infusion must be interrupted. The subject should be treated as clinically indicated with one or more of the following medications or interventions: antiemetics, antihistamines, analgesics, corticosteroids, leukotriene inhibitors, oxygen inhalation, epinephrine, bronchodilators, or other supportive measures as indicated.

Subjects with a Grade 3 infusion reaction may be discontinued from study drug at the discretion of the investigator, but must be discontinued if the Grade 3 infusion reaction recurs. Subjects with any Grade 4 infusion reaction are not eligible to receive additional elotuzumab.

If a patient's elotuzumab regimen is discontinued before the completion of cycle 2, he or she must come off protocol therapy. If elotuzumab is discontinued after completion of cycle 2, he or she can remain on protocol therapy.

Once the elotuzumab infusion-related reaction has resolved to  $\leq$  Grade 1, the infusion can be restarted at 0.5 mL/minute. If symptoms do not recur after 30 minutes, the infusion rate may be increased in a stepwise fashion (0.5 mL/minute every 30 minutes) to a maximum of 2 mL/minute or the rate at which the infusion reaction occurred, whichever is lower. Subjects who experience an infusion reaction require vital signs to be monitored approximately every 30 minutes for up to 2 hours after the end of the elotuzumab infusion. If the elotuzumab infusion reaction recurs, the infusion must be stopped and not restarted on that day. Appropriate therapy should be administered to address the subject's signs and symptoms. The infusion can be reattempted at the next protocol defined infusion time point at the investigator's discretion with additional premedication as described previously.

Infusion reactions after the completion of elotuzumab infusion: Should a  $\geq$ Grade 2 infusion reaction occur following completion of an elotuzumab infusion, the subject should be treated as clinically indicated with 1 or more of the following medications or interventions: diphenhydramine, acetaminophen, hydrocortisone, H2 inhibitor, leukotriene inhibitor, oxygen inhalation, epinephrine, bronchodilators, or other supportive measures as indicated.

Elotuzumab infusions on subsequent weeks after a prior Grade  $\geq$ 2 infusion reaction: Subjects with prior Grade 2 or higher infusion reactions should have future infusions started at 0.5 mL/min and then escalated in a stepwise fashion (0.5 mL/minute every 30 minutes). If no Grade  $\geq$  2 infusion reaction recurs, the escalation regimen may be resumed and the next infusion may be initiated as planned per the regimen.

If a patient experiences an infusion reaction of less than or equal to Grade 2, and the infusion reaction does not recur, the patient can resume elotuzumab administration at the rate at which the reaction occurred at the start of the next cycle at the investigator's discretion

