#### 2.9.5.3 Infusion Reactions

Treatment with therapeutic monoclonal antibodies is associated with infusion reactions with variable time of onset and varying levels of incidence and severity. As of March 2011 the key safety signal with elotuzumab is infusion reactions. As stated above, the definition of an infusion reaction for this analysis includes relevant signs and symptoms reported the day of or the day after elotuzumab infusion. The most frequent elotuzumab infusion reaction AEs regardless of causality across all Phase 1 studies included nausea, vomiting, chills, fever, flushing, dyspnea, cough, headache, dizziness, and rash. The majority of infusion reaction AEs were Grade 1 or 2 and resolved with little or no treatment. There was no apparent dose relationship for infusion reaction.

To minimize infusion reactions, all ongoing elotuzumab studies were amended in 2010, after the Grade 3 infusion AEs in the Phase 1 program (1701, 1702, and 1703Ph1), to ensure that all subjects receive premedication with IV corticosteroids, oral or IV diphenhydramine and oral acetaminophen prior to each elotuzumab infusion. As of 25-Mar-2011 all subjects treated in the Phase 2 expansion of Study 1703 have received this amended premedication regimen. Of the 73

CONFIDENTIAL

This document is confidential. Do not disclose or use except as authorized.

treated subjects, 56% of subjects experienced at least 1 Grade 1/2 infusion associated AE either the day of or the day after elotuzumab infusion. In contrast, 89% of subjects in the Phase 1 of Study 1703 (prior to new pre-medication regimen) experienced at least 1 infusion associated AE regardless of causality. Most infusion reactions occurred during the first cycle of therapy.

In summary, elotuzumab infusions have been associated with predominantly Grade 1 or 2 infusion reactions. All infusion reactions were managed by infusion rate changes and/or medications and almost all resolved the same day or within 24 hours. In most cases, subjects have been able to continue on study. Only 1 subject premedicated with diphenhydramine, acetaminophen, and IV corticosteroids prior to all doses of elotuzumab developed a Grade 3 infusion reaction related to elotuzumab and discontinued.

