### 5.2.2 Premedication Regimen in Subjects With a Prior Infusion Reaction

To be re-treated with elotuzumab, subjects with a prior infusion reaction must receive H1, H2 blockers and acetaminophen at maximum doses specified (e.g., 50 mg diphenhydramine, 50 mg ranitidine [or equivalent], and 1000 mg acetaminophen) 90-45 minutes before initiating the elotuzumab.

Doses of intravenous dexamethasone above 10 mg require a decrease in the oral dexamethasone. Recommended dexamethasone dosing is summarized below and in Table 3.

For subjects with prior Grade 2 infusion reaction, administer 10 mg IV dexamethasone (instead of 8 mg IV) as the premedication steroid 90-45 minutes before elotuzumab. Subjects should take 30 mg oral dexamethasone 24-3 hours before elotuzumab administration.

For subjects with Grade 3 or recurrent Grade 2 elotuzumab infusion reactions, consultation with the Principal Investigator is recommended. Administer 18 mg IV dexamethasone as the premedication steroid at least 45 minutes before elotuzumab. These patients should receive 8mg of oral dexamethasone 24-12 hours the day prior to elotuzumab administration. Then, administer 14 mg oral dexamethasone at most 3 hours prior to elotuzumab administration.

If a subject with a prior Grade 2 (recurrent) or 3 infusion reaction also requires dose reduction of oral dexamethasone, the dexamethasone dose on the days of elotuzumab infusion should be no less than 18 mg IV (on the day of elotuzumab infusion at least 45 minutes before elotuzumab).

Subjects with a Grade 4 infusion reaction are not eligible to receive additional elotuzumab. These subjects may continue to receive lenalidomide and dexamethasone. Subjects who experience an infusion reaction of any grade should be administered the recommended premedication for that reaction severity for the duration of the trial.

Subjects with prior infusion reactions may receive more aggressive pre-medications after discussion with the Overall Principal Investigator

CONFIDENTIAL

This document is confidential. Do not disclose or use except as authorized.

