## 6. DOSING DELAYS/DOSE MODIFICATIONS

### 6.1 Elotuzumab

No dose reductions for elotuzumab are allowed. If Elotuzumab is held on Day 1 of a new cycle, treatment with Lenalidomide/Dexamethasone will also be delayed. If Elotuzumab is held during any cycle on days 8, 15, or 22, the treating investigator will decide if Lenalidomide will be held using recommended guidance for retreatment below. Dexamethasone should always be given with Elotuzumab. The dose of dexamethasone may be modified per guidance below. Treatment may be delayed for a maximum of 21 days. If a patient must discontinue treatment with lenalidomide, they may continue to receive elotuzumab on study after discussion with the overall principal investigator.

If a patient must discontinue elotuzumab for unacceptable toxicity, they may continue to receive lenalidomide and dexamethasone on study after discussion and approval of the overall principal investigator.

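### For a Grade 4 infusion reaction before the end of cycle 2, section 5.2.2 lets lenalidomide and dexamethasone continue, while section 6.4.2 requires removal from protocol therapy

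*Combined protocol and SAP*

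**What the plan says.** Four places in the protocol bear on a patient who permanently stops elotuzumab early.

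- **Section 6.4.2 (infusion reactions of Grade 2 or higher).** On Grade 4: "Subjects with any Grade 4 infusion reaction are not eligible to receive additional elotuzumab". On timing: "If a patient's elotuzumab regimen is discontinued before the completion of cycle 2, he or she must come off protocol therapy". On later stopping: "If elotuzumab is discontinued after completion of cycle 2, he or she can remain on protocol therapy".
- **Section 5.2.2 (premedication after a prior infusion reaction).** It uses almost the same trigger: "Subjects with a Grade 4 infusion reaction are not eligible to receive additional elotuzumab". The next sentence reads: "These subjects may continue to receive lenalidomide and dexamethasone". No cycle is mentioned and no approval is required.
- **Section 6.1 (elotuzumab dose delays and modifications).** Patients who must stop elotuzumab for unacceptable toxicity are covered as follows: "they may continue to receive lenalidomide and dexamethasone on study after discussion and approval of the overall principal investigator". No cycle is mentioned here either.
- **Section 5.5 (criteria for coming off protocol therapy).** The list covers progression, intercurrent illness, unacceptable adverse events, non-compliance, withdrawal and change in condition. It has no item for stopping elotuzumab before the end of cycle 2.

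Section 13.1.1 puts every patient who received one dose of study treatment into the time-to-progression analysis, from which the 2-year progression-free rate is estimated.

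**The concern.** Sections 5.2.2 and 6.4.2 deal with the same event, a Grade 4 infusion reaction that ends elotuzumab. If it happens before cycle 2 is complete, they prescribe opposite outcomes for the other two drugs. A site working from one section would see no sign of the other rule.

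The choice affects what the patient receives and how the patient is observed. On protocol therapy, the study calendar measures serum disease markers on day 1 of each 28-day cycle. Off protocol therapy, section 5.6 calls for assessments every 3 to 6 months. A removed patient who then takes other myeloma-directed therapy leaves active follow-up and is followed for survival and subsequent therapy. Under 13.1.1, a patient without recorded progression is censored when last known to be progression-free. The section that a site follows can therefore influence when, or whether, progression is recorded for a patient who counts in the primary analysis in both cases.

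**Working it through.** The main check is a comparison of text. The plan states no figure for this point.

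**Step 1: one case under each section.** Take a Grade 4 infusion reaction on Cycle 1 Day 1.

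| Section | Elotuzumab | Lenalidomide and dexamethasone | Condition |
|---|---|---|---|
| 6.4.2 | Stops | Patient must leave protocol therapy | None |
| 5.2.2 | Stops | May continue | None |
| 6.1 | Stops, as unacceptable toxicity | May continue on study | Overall PI discussion and approval |
| 5.5 | Not addressed by cycle | Not addressed by cycle | Nearest item is unacceptable adverse events |

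Rows 1 and 2 cannot both be followed if the site uses the permission in 5.2.2. Row 3 depends on whether approval is available before the end of cycle 2, which no text states.

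**Step 2: does another passage settle it?** Section 6.4.3 and Table 6 cover elotuzumab that is delayed or held and later resumed, not permanent discontinuation. Neither 5.2.2 nor 6.1 refers to the cycle 2 cut-off, and 6.4.2 does not say that it overrides them.

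**Step 3: how many patients?** The direct conflict needs a Grade 4 reaction in cycle 1 or 2.

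- Study 1703 Phase 1 (section 2.9.5.1) treated 28 patients before the amended premedication. Two had serious reactions in the first cycle: one Grade 4 anaphylaxis and one Grade 3 stridor. The Grade 4 count is 1 of 28. For the planned enrolment of 55 (section 13.2): 55 × 1/28 = 1.96, about 2 patients.
- Study 1703 Phase 2 (section 2.9.5.2) treated 73 patients, all with the amended premedication. The most severe infusion reaction described is one Grade 3 rash, so the Grade 4 count is 0 of 73: 55 × 0/73 = 0.
- Zero of 73 does not prove a zero rate. The one-sided 95% upper bound is 1 − 0.05^(1/73) = 0.040, and 55 × 0.040 = 2.2 patients.

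The supported range is about 0 to 2 of 55.

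**Step 4: observation.** A patient kept on for all 24 cycles is on the cycle schedule for 24 × 28 = 672 days, most of the two-year window. A patient removed in cycle 1 would be on the 3-to-6-month schedule for nearly all of it.

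**The case against.** The strongest reply is that 6.4.2 is the only passage that addresses timing. It states both halves, before and after cycle 2, so it can be read as the specific rule that limits the general permissions elsewhere. Against 6.1 this has force. A permission that depends on approval fits with a rule under which approval is not available before the end of cycle 2, so 6.1 is ambiguous rather than clearly contradictory. Against 5.2.2 it is weaker. That section is equally specific about the event, has no approval step, and is not cross-referenced to 6.4.2.

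It may also be said that the two drugs could continue outside protocol therapy. But 6.4.2 describes a patient without elotuzumab after cycle 2 as still on protocol therapy, so the protocol treats the remaining drugs as part of it.

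Oversight also helps. Section 5.5 requires immediate notice to the Overall PI of life-threatening complications, so a Grade 4 reaction should reach one person. That lowers the risk of sites diverging, but leaves that person with two opposed rules.

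Three stronger readings are tempting and not supported.

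- A reader might infer that the conflict falls on the usual case, because section 2.9.5.3 says: "Most infusion reactions occurred during the first cycle of therapy". The same section describes these reactions as mainly Grade 1 or 2, with most subjects able to stay on study. Those reactions do not trigger the conflict.
- A reader might estimate 1 to 4 of 55 patients from 2 of 28 and 1 of 73 (55 × 2/28 = 3.9; 55 × 1/73 = 0.8). The 2 of 28 combine a Grade 4 and a Grade 3 reaction, both at 20 mg/kg and before the amended premedication, whereas this trial gives 10 mg/kg in cycles 1 and 2 with required premedication. The single premedicated patient who discontinued had a Grade 3 reaction. Section 2.9.5.3 gives no cycle for it and does not tie it to the 73.
- A reader might infer a choice between two years of two-drug therapy and no treatment. Dexamethasone is reduced in cycles 9 to 24, and removal means no protocol therapy, with alternative care to be discussed under 5.5.

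**Conclusion.** The inconsistency stands in a narrow form. For a Grade 4 infusion reaction before the end of cycle 2, sections 5.2.2 and 6.4.2 give opposed instructions, and nothing in the protocol says which governs. For other unacceptable elotuzumab toxicity in that window, 6.1 and 6.4.2 are ambiguous together.

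The likely size is about 0 to 2 of 55 patients. This assumes that the Grade 4 rates in Study 1703, in previously treated myeloma and partly at a higher dose, give a fair idea of this trial. An effect on the 2-year rate is possible through treatment received, assessment timing and censoring, but the documents do not allow it to be quantified. The sample size, decision rule and stated error rates do not depend on this wording. It is an inconsistency to correct, not a flaw in the design.

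**What to change.** Amend 5.2.2, 6.1 and 6.4.2 so that one rule governs permanent discontinuation of elotuzumab before the end of cycle 2. It should say whether the reason for stopping matters and whether Overall PI approval plays a part. Add the matching item or a cross-reference to 5.5. Which rule to adopt is for the sponsor and the investigators; no view is taken here.

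If patients have already met this situation, record which section was followed and list those patients alongside the primary analysis.

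The cost is a short text amendment. No sample size, threshold or analysis method changes.

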#### 6.4.3 Dose Delay or Interruption

If a patient's elotuzumab administration is delayed on day 1 of a cycle, both lenalidomide and dexamethasone will also be delayed until the elotuzumab is resumed, which would then become

CONFIDENTIAL

This document is confidential. Do not disclose or use except as authorized.

the new day 1 of that cycle.

If a patient's elotuzumab is held in the middle of a cycle, lenalidomide dosing will continue as scheduled. If the patient's elotuzumab is delayed during the cycle and is resumed within the designated window, (+/-3 days Cycles 1 and 2; +/-7 days Cycles 3 and beyond) the patient may receive that scheduled dose. If the elotuzumab is not resumed within the given window (+/-3 days Cycles 1 and 2; +/-7 days Cycles 3 and beyond), the patient is to omit that dose, and resume dosing at the next dosing time point. Dexamethasone should be held and resumed when Elotuzumab is held and subsequently resumed.

Patients may delay treatment for up to 3 weeks for elective surgeries and other non toxicity related events.

**Table 6: Dose Delay Instructions**

	To be resumed within window?	Lenalidomide	Dexamethasone	Elotuzumab
Elotuzumab delayed on Day 1 of Cycle	N/A	To be delayed until Elotuzumab is resumed	To be delayed until Elotuzumab is resumed	Resume dosing= new Day 1 of Cycle
Elotuzumab held on Day 8,15,or 22 of Cycle	Yes	Dosing to continue as scheduled	To be delayed until Elotuzumab is resumed	Resume dose any day within window; dose time point not skipped
Elotuzumab held on Day 8,15, or 22 of Cycle	No	Dosing to continue as scheduled	To be delayed until Elotuzumab is resumed	Resume dosing at next dosing time point (skip dose)

## 7. ADVERSE EVENTS: LIST AND REPORTING REQUIREMENTS

Adverse event (AE) monitoring and reporting is a routine part of every clinical trial. The following list of reported and/or potential AEs (Section 7.1) and the characteristics of an observed AE (Section 7.2) will determine whether the event requires expedited reporting **in addition** to routine reporting.

### 7.1 Expected Toxicities

#### 7.1.1 Adverse Events List(s)

##### 7.1.1.1 Adverse Event List of Elotuzumab

Treatment with therapeutic monoclonal antibodies is associated with infusion reactions with variable time of onset and varying levels of incidence and severity. The key safety signal with

CONFIDENTIAL

This document is confidential. Do not disclose or use except as authorized.

elotuzumab is infusion reactions. As stated above, the definition of an infusion reaction for this analysis includes relevant signs and symptoms reported the day of or the day after elotuzumab infusion. The most frequent elotuzumab infusion reaction AEs regardless of causality across all Phase 1 studies included nausea, vomiting, chills, fever, flushing, dyspnea, cough, headache, dizziness, and rash. The majority of infusion reaction AEs were Grade 1 or 2 and resolved with little or no treatment. There was no apparent dose relationship for infusion reaction.

#### 7.1.1.2 Adverse Event List for Lenalidomide

Events that have occurred in >10% of individuals treated with lenalidomide include neutropenia, anemia, thrombocytopenia, fatigue, rash, diarrhea, constipation, nausea, loss of appetite, itching, dry skin, muscle cramps, lack or loss of strength, dizziness, insomnia, swelling of the extremities, headache, back and joint pain, fever, cough, upper respiratory infection, and dyspnea.

Events that have occurred in >1% of individuals treated with lenalidomide include risk of DVT, PE, and blood clots that could lead to stroke, heart attack, or organ failure, febrile neutropenia, atrial fibrillation, pneumonia or lung infections, sepsis, dehydration and renal failure.

Events that have occurred in <1% of individuals treated with lenalidomide include rare treatment-emergent adverse events of angioedema, serious skin reactions including Stevens-Johnson syndrome (SJS) and toxic epidermal necrolysis (TEN) or an allergic skin reaction similar to that seen with thalidomide, tumor lysis syndrome (TLS), tumor flare reaction (TFR), and rhabdomyolysis. In addition, lenalidomide has been shown to increase the level of digoxin in the blood in some patients. Patients will be instructed to inform their doctor if taking digoxin.

There may be an increased risk of second cancers in patients who are on lenalidomide maintenance therapy after a bone marrow transplant.

